**Pilot Study: Electrical Stimulation via the
Scrambler Device as a Treatment for Restless
Legs Syndrome/Willis Ekbohm Disease**

NCT03249779

November 10, 2016

Pilot Study: Electrical Stimulation via the Scrambler Device as a Treatment for Restless Legs Syndrome/Willis Ekbohm Disease

Research Team:

(PI) [name].¹
[name].¹
[name], RPSGT¹
[name], R.N.²
[name].²

¹Center for Sleep Medicine, Mayo Clinic, Rochester, MN

²Division of Medical Oncology, Department of Internal Medicine, Mayo Clinic, Rochester, MN

Mayo Clinic IRB: 16-005286

Objectives: To evaluate, in a pilot fashion, efficacy and tolerability of electrical counter-stimulation using the Scrambler device in alleviating uncomfortable sensations and urge to move in patients with restless legs syndrome/Willis Ekbohm Disease (RLS/WED).

Hypotheses: Electrical stimulation applied to the lower extremities using the Scrambler device will improve discomfort and alleviate urge to move in patients with RLS/WED. This form of therapy will be well-tolerated and without significant side effects.

Background Information:

Clinical Description of RLS/WED

Restless legs syndrome/ Willis Ekbohm Disease (RLS/WED) is characterized by an unpleasant or uncomfortable urge to move the legs which comes on at rest and is at least partially alleviated by movement. Symptoms occur in the evening and nighttime hours¹. It is estimated that 7.2% of the Western population has RLS/WED, with 2.7% of the population experiencing moderate to severe symptoms.

RLS/WED has a significant negative impact on quality of life and is associated with anxiety and depression. Patients often experience significant sleep fragmentation due to symptoms which leads to daytime sleepiness and fatigue, cognitive symptoms, and loss of productivity at work².

One-third of RLS/WED patients require daily pharmacologic therapy to manage symptoms³. Patients with refractory symptoms often require multiple drugs of different classes⁴. Adverse effects from the most common agents used in treating RLS/WED include: drowsiness, dizziness, unsteadiness, weight gain, depression, augmentation, and development of impulse control disorders⁵⁻⁷.

Nonpharmacologic modalities are an important means of treating symptoms. Many nonpharmacologic strategies are based on counter-stimulation techniques to mask RLS/WED symptoms such as warm baths and massage. Sequential compression devices have been shown to be helpful in alleviating symptoms⁸. Nonpharmacologic counterstimulation modalities may be an important means of reducing medication burden in patients with RLS/WED and complementing pharmacotherapies in medically refractory patients.

Electrical Stimulation in the management of centrally driven neurogenic pain

Electrical stimulation has been utilized as an intervention in treatment of various forms of neurogenic pain (including peripheral neuropathy, trigeminal neuralgia, and multiple sclerosis). Much of the published data involves use of transcutaneous electrical nerve stimulation (TENS). TENS appears to work to reduce pain through both central and peripheral mechanisms. Animal and clinical studies demonstrate that the electrical impulses have a local effect on peripheral nerves to reduce pain at area of application. There also appear to be effects on central nervous system pathways (periaqueductal gray, medulla, and spinal cord) thus reducing pain at sites outside of the area of stimulation^{9,10}. The opiate and GABA receptors are implicated in the effects of TENS. These receptors are also targeted by pharmacologic therapies commonly used in RLS management. There are no good data regarding the efficacy of TENS for RLS.

Scrambler Therapy is a specific form of electrical stimulation which has also been utilized in chronic neurogenic pain¹¹. This modality of therapy differs from TENS in that the goal is to mediate the patient's perception of pain, rather than masking the peripheral pain signal. The results of this modality of treatment may be longer-lasting than TENS, presumably via reduction in central signal generation. Scrambler therapy works through C fibers to retrain the peripheral sensation in the area being treated. Further description of this technology is available at: International Patent PCT/IT2007/000647 and U.S. Patent No. 8,380,317. Literature search does not yield prior studies regarding efficacy of Scrambler therapy in treating RLS.

Multiple clinical trials have shown that electrical stimulation using Scrambler Therapy is an effective method of treating chronic neurogenic pain. Table 1 reviews the literature regarding the use of Scrambler Therapy in over 800 patients. Treatment is well tolerated and without significant side effects.

Electrical stimulation as a potential treatment of RLS/WED

Most patients with RLS/WED experience discomfort in the lower limbs which is described using terminology including: crawling, tingling, restless, electric, tension, and itching¹². The peripheral discomfort localized to the lower extremities in RLS/WED appears to be driven by a central mechanism. Functional neuroimaging studies have elucidated that RLS/WED stems from striatal dopaminergic dysfunction^{13,14}. This is corroborated by the positive response obtained when treating patients with dopaminergic medications¹⁵. The above data demonstrating efficacy of electrical

stimulation in other forms of centrally-mediated neurogenic pain, would suggest that this modality may also be an effective treatment in RLS/WED.

Significance: If electrical stimulation via Scrambler Therapy is effective in alleviating discomfort associated with RLS/WED, this may represent a novel nonpharmacologic modality of managing symptoms. Negative results will also be clinically useful in guiding strategies in the treatment of RLS/WED.

Proposed Study Design: Prospective, interventional, pilot study

Inclusion criteria:

- Male patients age 18 and over and post-menopausal women (or women who are not of child-bearing potential) diagnosed with RLS/WED by a board certified sleep medicine physician within the Mayo Clinic Center for Sleep Medicine.
- Patients must have moderate to severe symptoms which have been present for \geq 3 months. Patients must endorse discomfort as part of their typical RLS/WED symptomatology.
- Patients must experience daily symptoms and must experience daily symptoms during afternoon hours (12-5 PM)
- Patients on no medications for RLS/WED, or those who have refractory symptoms despite RLS/WED medications will be enrolled. Patients on alpha-2-delta ligands (pregabalin, gabapentin) will be asked to discontinue these medications two weeks prior to starting treatments and remain off these medications throughout the study protocol.
- Informed consent to participate in this study needs to be obtained

Exclusion criteria:

- Research authorization not provided
- Patients who are asymptomatic (either by verbal report or completion of severity scale) at time of initiation of Scrambler Therapy treatment
- Patients who have made changes in medication regimen during the 2 weeks prior to study initiation (including initiation of iron supplementation)
- Prior use of Scrambler Therapy
- Female patients of child-bearing potential (those who are not post-menopausal or post-hysterectomy)
- Patients with implantable drug delivery systems, heart stents, or metal implants (including pacemakers and defibrillators)
- Patients with history of epilepsy or other medical conditions that in the opinion of the investigators should be excluded
- Patients with skin conditions or wounds in or around the area of electrode application (lower extremities)
- Patients treated with alpha-2 delta ligands (gabapentin, pregabalin), who cannot discontinue the medications as above

Proposed Methods:

A total of up to 10 eligible subjects will be recruited who have been diagnosed with chronic RLS/WED in the Mayo Clinic Center for Sleep Medicine. Subjects must experience daily symptoms and must typically be symptomatic during the timeframe in which Scrambler Therapy will be utilized (12-5 PM). Each patient will complete the International Restless Legs Syndrome Rating Scale (IRLS), a validated scale which assesses severity of RLS symptoms¹⁶ at baseline (pre-treatment) and before and directly after each session of Scrambler Therapy.

Patients will receive Scrambler Therapy (Appendix VI) on a daily basis for up to 10 consecutive weekdays. Electrodes will be placed proximal to the area of RLS symptomatology, with gradual downward localization until the entire area of RLS symptoms has been treated. Treatment will initially take place on one leg. Treatments will be administered by a technician trained in using the Scrambler device. A physician or nurse (with familiarity of Scrambler therapy) will be available throughout each treatment session.

Patients will complete questionnaires regarding discomfort or other side effects encountered during or after treatment. They will also complete surveys assessing for any changes (benefits or worsening) in RLS symptomatology between treatments.

Patients will be monitored for any adverse events associated with the study procedures. Any reported adverse events will be expediently classified by the study group as to severity level, whether it relates to the treatments in the study protocol, and whether the event was expected or unexpected. This information will allow determination of whether or not the adverse event should be reported as an expedited report or part of the routinely reported outcomes data. All adverse events which meet criteria for expedited reporting will be reported to the institutional IRB as well as external agencies as required.

If there is no evidence of clinical benefit with the first 2-4 patients, then further patients may not be recruited.

Test schedule:

| Tests and procedures | | | | | |
|---|--------------------------------|-------------------------|---|------------------------|---------------------------|
| | ≤30 days prior to registration | Day 1, Prior to therapy | Daily for 10 consecutive week days beginning on Day 1 of active therapy | On last day of therapy | 1 Week after last Session |
| Clinical visit with history and exam, Eligibility questions, Consent | X | | | | |
| Baseline severity question confirming moderate to severe symptoms | X | | | | |
| IRLS severity questionnaire regarding the prior week (Appendix I) | | X | | X | X |
| Patient Questionnaire: Just Before Each Treatment (Appendix II) | | X | X | | |
| Patient Questionnaire: Just After each treatment (Appendix III) | | | X | | |
| Patient Questionnaire After each therapy and during weekly follow-up: Global Impression of Change and Patient Preference (Appendix IV) | | | X | | |
| Daily Treatment Log and Adverse Assessment (Appendix V) | | | X | | |
| Coordinator phone call to discuss therapy and any concerns, record any adverse events that are reported and to remind the patient to complete questionnaire and mail back | | | | | X |

Funding:

Small Grant Award through CCATS and Division of Pulmonary Medicine – for research coordinator support and subject remuneration

References:

1. American Academy of Sleep Medicine. *The international classification of sleep disorders : diagnostic and coding manual*. 2nd ed. Westchester, Ill.: American Academy of Sleep Medicine; 2005:xviii, 297 p.
2. Stevens MS. Restless Legs Syndrome/Willis-Ekbom Disease Morbidity: Burden, Quality of Life, Cardiovascular Aspects, and Sleep. *Sleep medicine clinics*. 2015;10:369-373, xv-xvi.

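### The stability exclusion covers only medication, so a compression device or similar non-drug therapy started shortly before or during the study could be read as Scrambler benefit

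*Protocol*

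**What the plan says.** All references are to the protocol.

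- **Stability before entry.** The Exclusion criteria bar "Patients who have made changes in medication regimen during the 2 weeks prior to study initiation (including initiation of iron supplementation". This is the only stability rule. The one non-drug treatment named in the criteria is the test treatment itself: "Prior use of Scrambler Therapy".
- **Other therapy on study.** The Inclusion criteria require patients on gabapentin or pregabalin to stop two weeks beforehand and "remain off these medications throughout the study protocol". Nothing else in the criteria, the Proposed Methods or the Test schedule restricts other RLS therapy, and no schedule row names non-drug therapy.
- **What the Background says about non-drug therapy.** On compression: "Sequential compression devices have been shown to be helpful in alleviating symptoms". On baths and massage: "Many nonpharmacologic strategies are based on counter-stimulation techniques to mask RLS/WED symptoms such as warm baths and massage". On TENS: "There are no good data regarding the efficacy of TENS for RLS".
- **Design and size.** "Proposed Study Design: Prospective, interventional, pilot study", with no control or sham arm described, and "A total of up to 10 eligible subjects will be recruited". Recruitment may stop if the first 2-4 patients show no benefit.
- **Measures.** The Test schedule places the prior-week IRLS at Day 1, the last day of therapy and one week later. Separate questionnaires are completed before and after each session, together with a global impression of change and a daily log. The Proposed Methods add surveys of symptom change between treatments.

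**The concern.** By excluding recent medication changes, and naming iron, the protocol accepts that a recent change in other therapy can distort the before/after comparison. It does not apply that reasoning to non-drug therapies, although its Background credits one of them (compression) with relieving symptoms and describes others as masking them. A patient who began nightly compression a few days before Day 1, or begins it during the treatment fortnight, meets the criteria as written.

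Efficacy is read from change within each patient, so nothing in the design separates the effect of such a therapy from that of the Scrambler. Later analysis cannot repair this if the start was neither restricted nor recorded. The protocol enrols patients with refractory symptoms and asks some to stop a drug two weeks beforehand. It is a reasonable inference, though not a stated fact, that some of these patients would look for non-drug relief in the same period.

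**Working it through.** There is no figure in the protocol to reproduce. The check has three parts: coverage of the rules, exposure of the prior-week IRLS, and exposure of the session questionnaires.

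**1. Coverage of the rules**

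| Other therapy | Protocol's view of its effect in RLS | Stability rule before entry | Rule on study |
|---|---|---|---|
| Medication, including iron | Drugs used to manage symptoms | Yes, 2 weeks | Only for gabapentin and pregabalin |
| Sequential compression | Relieves symptoms | None | None |
| Baths, massage | Mask symptoms | None | None |
| TENS | No good data | None | None |

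**2. Exposure of the prior-week IRLS**

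Inputs from the Test schedule and Proposed Methods: IRLS at Day 1, at the last session (Day L) and one week later; up to 10 consecutive weekdays of treatment.

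Length of a full course: a Monday start crosses one weekend, so L = 10 + 2 = 12. Any other weekday start crosses two, so L = 10 + 4 = 14.

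Assumptions: the recall week is the seven days ending the day before the questionnaire; study initiation means Day 1; the other therapy is used daily and acts at once.

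- Start d days before Day 1: exposed days in the baseline week = min(d, 7); in the final week = 7.
- Start on Day s of the study: exposed days in the baseline week = 0; in the final week = min(L − s, 7), or 0 if s = L.
- Start t days after the last session (t up to 7): exposed days in the follow-up week = 7 − t. For any start on or before Day L this is 7.

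| Start of the other therapy | Baseline week | End-of-therapy week | Excess, end minus baseline | Follow-up week |
|---|---|---|---|---|
| 7 to 14 days before Day 1 | 7 of 7 | 7 of 7 | 0 days | 7 of 7 |
| 5 days before | 5 of 7 | 7 of 7 | 2 days | 7 of 7 |
| 3 days before | 3 of 7 | 7 of 7 | 4 days | 7 of 7 |
| Day 1 | 0 of 7 | 7 of 7 | 7 days | 7 of 7 |
| Day L − 7 (Day 5 or 7) | 0 of 7 | 7 of 7 | 7 days | 7 of 7 |
| Day L − 3 (Day 9 or 11) | 0 of 7 | 3 of 7 | 3 days | 7 of 7 |
| Day L | 0 of 7 | 0 of 7 | 0 days | 7 of 7 |

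The exposure comes from starts in the last days before Day 1 and from starts on study. Starts 7 to 14 days before largely cancel unless the effect builds up over time. These are counts of exposed days, not estimates of bias, because the protocol gives no effect size for any of these therapies and no frequency of use.

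**3. Exposure of the session questionnaires**

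If another therapy shifts both readings of a session by the same amount b, the within-session change is (post + b) − (pre + b) = post − pre. The change within a session is therefore largely protected. A trend in the pre-session readings from one day to the next is not.

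**The case against.** Much can be said against making more of this, and several of these points stand.

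- **TENS.** A reader might infer that the protocol regards all counter-stimulation, TENS included, as effective in RLS. It does not. It reports no good TENS data in RLS, and its remarks on TENS acting away from the stimulated site concern neurogenic pain. Only compression is described as shown to help. The protocol also says that the Scrambler aims to alter perception of pain, not to mask it, so these therapies cannot simply be equated with the test treatment.
- **All the efficacy evidence.** A reader might infer that every outcome is compromised. Part 3 of the working shows otherwise for change within a session.
- **A percentage at risk.** It is tempting to say that one patient is a tenth of the cohort, or a quarter to a half of the evidence at the 2-4 patient look. Those are headcounts. Stable, long-standing use largely cancels, and the number of new starters is not given.
- **Existing filters.** Patients need daily, moderate to severe symptoms lasting at least 3 months and must not be symptom-free when treatment begins. This keeps out a patient whose new device already worked fully. It does not keep out a partial responder or someone who starts a device on study.
- **Recording.** The contents of Appendices II to V are not shown, so the log may already capture other therapies. It cannot be said that recording is absent, only that nothing in the text provides for it. Recording would help attribution but would not replace a stability rule.
- **A small uncontrolled pilot.** Placebo response and natural fluctuation are just as inseparable here, and this change would not address them. That limits the benefit but does not remove it: this source of confusion, unlike those two, can be reduced with one criterion and one form line.

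**Conclusion.** The concern holds in a limited form. Followed exactly, the stability exclusion admits patients who have just started a non-drug therapy that the protocol itself says relieves symptoms, and nothing stated prevents or expressly records a start during the study. With no described comparator, the benefit could be credited to the Scrambler on the prior-week IRLS, the between-treatment surveys and the global impression of change, and much less so on change within a session. The critical period runs from the last days before Day 1 to the one-week follow-up.

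The size is unknown. It depends on how many patients start or change such a therapy and how well it works for them, and the protocol gives neither. The conclusion assumes that Appendices II to V contain no stability rule. The documents do not support saying that the pilot's efficacy reading is invalid or that a stated share of it is at risk. This is a cheap improvement worth making before enrolment, and not a contradiction in the plan.

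**What to change.** 1. Extend the existing two-week stability exclusion to non-drug RLS therapy that has been newly started or changed, chiefly compression or other devices.
2. Because that criterion does not reach starts on study, record any start or change of non-drug RLS therapy, and of medication, at baseline, on the daily log and at the one-week call. If the forms not shown already do this, a reference to them is enough.
3. Report the before/after change with and without the patients who had such a start or change. With up to 10 patients this can be a simple listing beside the two summaries.

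Whether to restrict ordinary self-relief such as baths or massage during the study is for the investigators to decide; the record in step 2 is useful either way.

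Cost: a few volunteers enter up to two weeks later, and one more line is completed on an existing form.

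### After the last session, adverse events other than RLS severity rest on one coordinator call with no adverse-event form marked, although tolerability is a co-objective

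*Protocol*

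**What the plan says.** The Objectives section sets out to evaluate "efficacy and tolerability of electrical counter-stimulation using the Scrambler device". The Hypotheses section adds: "This form of therapy will be well-tolerated and without significant side effects". Tolerability is thus one of two things the study is meant to establish.

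Harms data are described in three places.

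- **Proposed Methods, questionnaires:** "Patients will complete questionnaires regarding discomfort or other side effects encountered during or after treatment". No appendix is named.
- **Proposed Methods, safety paragraph:** "Patients will be monitored for any adverse events associated with the study procedures". No end date is given.
- **Test schedule:** the row that opens "Daily Treatment Log and Adverse Assessment (Appendix V" has a mark only in the daily column. So does the questionnaire completed just after each treatment (Appendix III). The column for one week after the last session has two marks: the IRLS, which asks about the preceding week, and a coordinator call. In the call the coordinator talks over the therapy and any concerns, is to "record any adverse events that are reported", and reminds the patient to return the questionnaire by mail.

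Treatment is given "on a daily basis for up to 10 consecutive weekdays", and "A total of up to 10 eligible subjects will be recruited". There is one arm and no control.

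**The concern.** The way harms are collected appears to change when treatment ends. During treatment, each session carries a named adverse assessment and a questionnaire. If an effect appears after the patient has gone home from any session but the last, the next session gives a scheduled occasion to record it. After the last session there is no next session, and the one remaining contact has no adverse-event form attached to it.

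If a call that records what the patient brings up finds fewer events than the items of a form would, events after treatment are recorded less completely than events during it. The difference runs in one direction, towards the hypothesis of good tolerability. With at most 10 uncontrolled patients, a single unrecorded event can change what is said about tolerability, and no later analysis can restore data that were not collected.

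**Working it through.** The Protocol states no adverse-event rate and no calculation for tolerability, so there is no figure of its own to reproduce. The check is a reading of the schedule, a day count and one labelled illustration.

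**1. Schedule, row by row**

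| Instrument | Daily treatment column | One week after last session |
|---|---|---|
| Appendix V, adverse assessment | marked | not marked |
| Appendix III, just after treatment | marked | not marked |
| IRLS, preceding week | not marked (has its own marks on Day 1 and the last day) | marked |
| Coordinator call | not marked | marked |

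Efficacy has a structured scale at one week. Tolerability has the call, plus whatever the IRLS shows about worsening of RLS itself. The Appendix IV row is titled as if it were also used at weekly follow-up, but it has no mark in the one-week column. It concerns global change and preference, so it would not fill the gap in any case.

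**2. How long the affected interval is**

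Input: 10 consecutive weekdays, then a contact 7 days after the last session.

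- Monday start: last session on calendar day 12, call on day 12 + 7 = 19. Share of the observed time: 7/19 = 36.8%.
- Tuesday to Friday start: last session on day 14, call on day 14 + 7 = 21. Share: 7/21 = 33.3%.

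A completer has 10 scheduled Appendix V assessments during treatment and none in the following week.

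**3. Patients who stop early**

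Take a stop after 3 sessions. The last session falls on day 3 to 5, depending on the starting weekday, and the call on day 10 to 12. The interval from last session to call is again 7 days, because the contact is tied to each patient's own last session.

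The number of Appendix V assessments depends on how the daily column is read:

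- at sessions only: 3;
- literally, for ten weekdays from Day 1: 10.

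The form's title, a treatment log, favours the first reading, but the Protocol does not settle it.

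**4. Illustration: how sensitive a ten-patient result is to capture**

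Assumptions, none of them from the Protocol: 20% of patients truly have a post-treatment event, and a share s of those patients have it recorded. Then

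P(at least one patient recorded) = 1 − (1 − 0.20 × s)^10.

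| s | Calculation | P |
|---|---|---|
| 1 | 1 − 0.80^10 | 89.3% |
| 0.75 | 1 − 0.85^10 | 80.3% |
| 0.5 | 1 − 0.90^10 | 65.1% |
| 0.25 | 1 − 0.95^10 | 40.1% |

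This shows only that, with 10 patients, completeness of capture matters for whether an event is seen at all. It does not estimate s for the planned call.

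**The case against.** The strongest reply is that the Protocol does collect post-treatment harms. The call is scheduled and made by staff, and it opens with the therapy and the patient's concerns, so it is a prompt rather than passive waiting. The safety paragraph speaks of reported events for the whole study, so the wording of the call row may be no more than the Protocol's usual vocabulary. The one-week IRLS covers exactly the 7 days in question, so worsening of RLS, a plausible delayed harm, is measured with a validated scale. The contents of Appendices II to V are not in the text at hand; if Appendix V is an open log, it may differ little from the call. The promise of side-effect questionnaires can also be read as referring to the time just after each session, in which case the schedule does not contradict it. Finally, the exact questions for a call are often left to a case report form or a coordinator script.

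Most of this stands, and it limits the point. It rules out saying that the call is the only post-treatment assessment or that harms go uncollected. It does not remove the difference in method: for anything other than RLS severity, a form is named during treatment and none is named afterwards. Which assessments are scheduled, and when, is fixed in the Protocol.

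A reader might also infer that the loss is greatest in patients who stop early, perhaps because they tolerated treatment poorly. The Protocol does not support this. The interval is 7 days for everyone. It is a larger share of an early stopper's observed time only because the treatment period is shorter. Whether such a patient has fewer Appendix V assessments depends on a column heading that can be read either way.

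**Conclusion.** The point holds as a risk, not as a demonstrated loss. For a completer, one third or slightly more of the observed time (33% to 37%) has no adverse-event form scheduled, against 10 Appendix V assessments during treatment, and tolerability is a co-objective in at most 10 patients. Harms after the final session may therefore be less completely recorded than harms during treatment, which would favour the tolerability hypothesis.

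The number of events missed cannot be derived, because the Protocol gives neither an event rate nor a capture rate; any percentage would only restate an assumed capture rate. The conclusion assumes that Appendix V, whose content is not shown, asks more specifically than the call would. This is a low-cost improvement to harms ascertainment, not an error that undermines the study.

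**What to change.** - Mark Appendix V in the column for one week after the last session.
- Reword the call row so that the coordinator asks the Appendix V adverse-event items about the whole interval since the last session and records the answers.
- State that this applies to every patient, including those who stop before 10 sessions. That settles what early stoppers complete at the one-week contact.
- Report adverse events separately for the treatment period and the post-treatment week.

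The cost is one mark in the schedule, one reworded row and a few more minutes in a call already planned, with no new visit, staff or procedure. The downside is that more minor events will be recorded, so the tolerability result may look slightly less favourable.
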